## 7 ASSESSMENTS

**Table 1. Protocol Activity by Visit**

Protocol Activity	Screen/ Baseline	Visit 1	Follow-up 1	Follow-up 2	Follow-up 3	Follow-up 4 (Final)
		Day 1	Day 7 $\pm$ 5 business days	Day 14 $\pm$ 5 business days	Day 21 $\pm$ 5 business days	Day 28 $\pm$ 5 business days
Week (approximate)	0	1	2	3	4	5
Visit #	0	1	2	3	4	5
Informed Consent	X					
Interview and Medical History	X					
Pregnancy Test (females of childbearing potential)	X					
Randomization	X					
DLMO	X					X
Daily sleep diary	X	X	X	X	X	X
Wrist actigraphy	X	X	X	X	X	X

Melatonin Treatment		X	X	X	X	X
Adverse Event Assessment			X	X	X	X
Concomitant Medication Assessment	X	X	X	X	X	X
Daytime functioning and sleep self-report measures	X					X

## 7.1 Primary Endpoint Assessments

Protocol activity and assessments are summarized in Table 1 above.

Primary endpoint: change in the time of DLMO from pre- to post-treatment.

To assess time of DLMO, all eligible participants (regardless of group assignment) will undergo in-home salivary DLMO collection at pre- and post-treatment, using the protocol established by [name] (Co-I) ([name] et al. 2015). Participants will be oriented to the collection procedures during their clinic visit. Participants will be in dim light starting 30 minutes prior to the first sample collection. Collection begins 6 hours prior to participants' habitual sleep onset per their most recent week of actigraphy at baseline. At post-treatment, collection begins 6 hours prior to participants' bed time as assigned at the final treatment session. Samples are collected via Salivette every 30 minutes until bedtime (13 samples total). They are provided with a kit, which includes: a checklist of procedures; a test tube rack; a toothbrush; a nightlight; blue-blocking Uvex glasses (with an Actiwatch attached to monitor compliance of use); an iPod programmed to alarm at collection times; a light medallion (an Actiwatch with light sensor worn around the neck to monitor compliance with light exposure); Salivette collection vials equipped with Track Cap, which will record when the vial was opened; and a label dispenser with pre-labeled labels. Participants wear the blue-blocking glasses throughout the dim light saliva collection and are required to remain seated in the 10 minutes before each sample. When the iPod alarms, participants brush their teeth without toothpaste, collect saliva by chewing on the Salivette, and deposit it in the vial. Participants are informed about the compliance measures utilized in the study. Samples will be stored in participants' freezers until they can be transported to our facility. Samples are centrifuged for two minutes, frozen, and assayed using Bühlmann Laboratory radioimmunoassay (ALPCO Diagnostics, Salem, NH) at **Solidphase Inc.** To ensure consistency and to minimize the effects of sleep schedule changes on the weekends/days off of work, whenever possible, all participants will complete DLMO collection on the third night of their typical workday sleep schedule (e.g., DLMO collection will occur on a Wednesday, Thursday, or Friday night for participants who work a traditional Monday-Friday schedule).

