### 1.2 Background and Rationale

#### **Delayed sleep-wake phase disorder is common and debilitating**

The most common circadian rhythm sleep-wake disorder, delayed sleep-wake phase disorder (DSWPD) is estimated to affect up to 7-16% of adolescents and young adults, and more than 10% of patients presenting to sleep clinics with insomnia symptoms (American Academy of Sleep Medicine 2014). The prototypical patient with delayed sleep-wake phase disorder presents with chronic difficulty falling asleep and waking at required or socially desired times (American Academy of Sleep Medicine 2014). When free to select their own sleep schedule, patients with DSWPD have significantly later sleep onset and wake times relative to convention, with preserved sleep quality and normal sleep duration (American Academy of Sleep Medicine 2014). Delay of the circadian timing system relative to the required or socially desired timing of the sleep episode is posited to be one of the major etiological factors (Micic et al. 2016). This is corroborated by numerous studies, which show delays ranging from 2-6 h in DSWPD patients' circadian phase relative to normal sleepers (Oren et al. 1995, Ozaki et al. 1996, Shibui et al. 1999, Uchiyama et al. 2000, Watanabe et al. 2003).

The inability to maintain a sleep-wake schedule consistent with social and occupational requirements often leads to chronic sleep loss and significant daytime impairments. Consequences of DSWPD are wide-ranging and include absenteeism and presenteeism, and impairment in social and family life (Rajaratnam et al. 2015). Indeed, role disability is greater, and quality of life is more impaired, in adults with DSWPD relative to other chronic disorders, including sleep apnea, migraine, and depression (Nagtegaal et al. 2000).

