### **2.2.1 Primary Endpoint**

The primary endpoint is change in time of DLMO from pre- to post-treatment.

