## **3 STUDY DESIGN**

### **Overview of research design**

This study is a randomized, controlled, parallel double-blind 4-week trial of 0.5 mg of exogenous melatonin (Emens et al. 2015) timed to either 3 h before actual DLMO based on in-home measurement (M-DLMO, n = 25) or 3 h before DLMO estimated at 2 h before average sleep onset time based on actigraphy and sleep diary (E-DLMO, n = 25). Note that the intervention tested is the method used to time melatonin administration--not melatonin per se, as all participants will receive the same dose of melatonin for the duration of the study.

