## 5 STUDY TREATMENTS

### 5.1 Allocation to Treatment

Eligible participants will be randomized using the minimization method (Pocock et al. 1975) in a 1:1 ratio to M-DLMO or E-DLMO. Assignment to condition will be balanced by age and baseline sleep onset time on free days. For allocation of participants, a computer program (the Treatment Assignment System, created by UM's Consulting for Statistics, Computing, and Analytics Research) will be used by the study coordinator to generate the group assignment at enrollment for each participant.

Participants will be blinded to the specific study hypotheses and to their group assignment. The study clinician will be blinded to group assignment. The study coordinator, who communicates the time of melatonin administration to the study clinician, will not be blinded to the actual DLMO of participants in the M-DLMO condition; however, they will be blinded to the actual DLMO of participants in the E-DLMO condition until their participation is complete.

Due to individual variation in melatonin levels or errors in the saliva collection process, it is possible that DLMO will not be able to be determined for a small proportion of participants. To retain these participants in the protocol, if they are randomly assigned to the M-DLMO condition, the study coordinator may change their assignment to the E-DLMO condition. Data for these participants will be examined post-hoc upon completion of the study using sensitivity analyses before determining whether to retain or discard their data from analyses.

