#### **6.2.1 Follow-up (Weeks 1-4)**

Participants will continue to take melatonin 0.5 mg at the scheduled time daily for the 4 weeks of the study. At approximately Week 1, they will be provided with an additional 14-

day supply of melatonin. Each follow-up session (approximately Weeks 1-4) will follow an identical protocol:

1. Study staff will meet with the participant to query the following: review previously reported medications and current use of previously reported medications; any new medications; any side effects from the melatonin; any unexpected medical conditions since their last visit; any new medical diagnoses or changes in medical history since their last visit. They will also meet with the participant to download their actigraphy, TrackCap data, and complete a pill count. Compliance with melatonin administration timing per TrackCap, the pill count, changes in medical history or medications, and side effect information, will be provided to the study clinician. Only melatonin administration deviations  $\geq$  30 minutes will be considered non-compliant and be reported as protocol deviations.
2. During the follow-up treatment session, the study clinician will review side effects/adverse events, compliance with bed and wake times, adherence to melatonin administration time, and address any barriers to compliance. Participants will be instructed to advance the time of melatonin administration by 1 h and their bed-wake schedule by 1 h (without altering their total time in bed from their baseline average) at each weekly treatment session until they reach their desired bed-wake schedule. The study clinician may also choose to adjust the melatonin administration time or time in bed schedule using their discretion and clinical judgement as needed. At each follow-up session, participants will be provided with a handout summarizing the main components of the session.

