#### ***9.2.1 Analysis of Primary Endpoint***

Change in DLMO from pre- to post-treatment will be calculated in minutes for each participant. A 2-tailed t-test will evaluate the difference between the change in DLMO between the two groups.

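### The primary t-test has no rule for a post-treatment DLMO outside the saliva window, although that window ends at a bedtime moved earlier during treatment

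*Combined protocol and SAP*

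**What the plan says.** - **Endpoint and test.** Section 2.2.1: "The primary endpoint is change in time of DLMO from pre- to post-treatment". Section 9.2.1 says that the change "will be calculated in minutes for each participant. A 2-tailed t-test will evaluate the difference between the change in DLMO between the two groups". It has no provision for a participant whose post-treatment onset was not captured.
- **Sampling window.** Baseline collection starts 6 h before habitual sleep onset by actigraphy. Post-treatment collection is set by the assigned bedtime instead (section 7.1): "bed time as assigned at the final treatment session. Samples are collected via Salivette every 30 minutes until bedtime (13 samples total".
- **Assigned bedtime.** Under section 6.2.1, melatonin time and the bed-wake schedule both advance by 1 h "at each weekly treatment session until they reach their desired bed-wake schedule. The study clinician may also choose to adjust the melatonin administration time" or the time in bed.
- **Interval from DLMO to sleep onset.** Section 3 times the E-DLMO arm at "3 h before DLMO estimated at 2 h before average sleep onset time". The plan's working interval is thus 2 h.
- **Nearest rule.** Section 5.1 discusses a DLMO that cannot be determined and lets the coordinator move such M-DLMO participants to E-DLMO. That can only concern the baseline DLMO, which sets treatment time. Even there, the data are to be "examined post-hoc upon completion of the study using sensitivity analyses before determining whether to retain or discard their data from analyses".

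**The concern.** The last saliva sample is tied to a clock time that the intervention itself moves. A participant whose bedtime moved well forward, but whose melatonin rhythm did not follow, can reach the last sample before onset. That participant has responded poorly on the primary endpoint, and the plan assigns no value.

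Several readings are open: exclude the participant, substitute the last sample time, or model the value as censored. They give different answers from the same data. If the t-test is simply run on the changes that can be calculated, the smallest advances drop out first. Under Hypothesis 1 the E-DLMO arm advances less, so it would lose more participants and the difference the trial seeks would shrink. If clinicians move bedtimes differently in the two arms, exclusion can also produce a difference where none exists.

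**Working it through.** **The plan's own figures.** Window: 6 h ÷ 30 min + 1 = 13 samples, as section 7.1 states. Section 9.1 gives 23 per group for 1 h, 90% power and alpha 0.05, but no SD. Solving the two-sided two-sample t-test for the SD gives 61.4 min (62.8 min by the normal approximation). With 61 min, 25 per group has 92% power if nobody is lost. The margin of 25 over 23 covers 2/25 = 8% loss.

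**When an onset is missed.** Let S be baseline sleep onset, g the DLMO-to-sleep-onset interval, a the true advance, and k the shift of the assigned bedtime counted from S, all in hours.
- Post-treatment DLMO = S − g − a. Window = S − k − 6 to S − k.
- Too late to be seen: a < k − g. With g = 2, a 3 h shift hides advances under 1 h.
- Already past at the first sample: a > k + 6 − g.

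**Assumptions, none given in the documents except the mean of g.** g has mean 2 h (section 3) and SD 0.75 h. The advance has SD 61 min = 1.017 h in both arms. The true difference is 60 min, with mean advances (E vs M) from 2 vs 3 h to 1 vs 2 h. k is the same for everyone.

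**Worked case: k = 3, means 1 vs 2 h.** The SD of g + a is √(0.75² + 1.017²) = 1.263 h. The late share is Φ((k − 2 − m)/1.263):
- E-DLMO: Φ(0) = 50%. M-DLMO: Φ(−0.792) = 21%.

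The mean advance among those observed is m + (1.017²/1.263) × φ(z)/(1 − Φ(z)), with z = (k − 2 − m)/1.263. Early onsets are negligible here.
- E-DLMO: 1 + 0.818 × 0.798 = 1.653 h = 99 min.
- M-DLMO: 2 + 0.818 × 0.371 = 2.304 h = 138 min.
- Difference: 138 − 99 = 39 min, against a true 60.

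**Exclusion over the range** (simulated trials, 25 per arm, both ends of the window applied):

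| k | late, E-DLMO | late, M-DLMO | early, largest share | difference | power |
|---|---|---|---|---|---|
| 1 h | 1-6% | 0-1% | 6% (M-DLMO) | 54-55 min | about 89% |
| 2 h | 6-21% | 1-6% | 1% | 48-54 min | 79-89% |
| 3 h | 21-50% | 6-21% | under 1% | 39-48 min | 53-79% |

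Early onsets matter at k = 1 with means of 2 vs 3 h. Ignoring them would give 59 min instead of 54.

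**Other handling.** Substituting the last sample time for late onsets gives 53-58 min and 90-92% power at k = 2, and 39-53 min and 80-90% at k = 3. Censored-normal regression recovers about 60 min in these cases, with power about 92% at k = 1-2 and 86-92% at k = 3.

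**If the shift tracks response** (k = advance, or advance + 1 h, rounded, with noise of SD 1 h, limited to 0-4 h): exclusion gives 60-62 min and 87-91% power.

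**Spread of g** (k = 3, 1 vs 2 h): SD 0 gives 29 min and 42% power; SD 1.0 h gives 43 min and 58%.

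**No true difference.**
- Same SD and same k in both arms: no bias.
- Mean advance 1 h in both arms, k = 2 in one and 3 in the other: observed means are 78 and 99 min, so the bias is 21 min, with about 20-21% false positives. The sign follows the arm with the larger shift. The censored model gives about 0 min and 4%.
- Equal means, one arm with SD 1.5 h, k = 3: exclusion bias is 12-25 min toward the more variable arm. A common-SD censored model leaves 2-14 min, an arm-specific-SD model about 0-2 min.

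**The case against.** **The worst figures are one unfavourable cell.** They need everyone shifted 3 h, a shift unrelated to response, and an E-DLMO advance averaging only 1 h. Section 6.2.1 moves melatonin and bedtime together, stops at the desired schedule and allows clinical judgement, so shift and response may well be linked. This stands, which is why the result is given as a range. The link is not assured, however. Table 1 schedules DLMO only at baseline and the final visit, so nobody sees an interim DLMO, and the default stopping point is the desired schedule rather than circadian response.

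**Frequency cannot be determined.** This also stands. The weekly rule allows three or four 1 h steps, but they run from the bedtime set at Visit 1, which the documents do not equate with baseline sleep onset. A reader might take section 1.2, on studies "which show delays ranging from 2-6 h in DSWPD", as the size of the shift. That passage describes circadian delay relative to normal sleepers, not a planned change in bedtime.

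**The cited collection protocol may hold a convention.** Section 7.1 relies on a published procedure that cannot be consulted here. It may say how an unreached onset is scored. If so, 9.2.1 should state that convention and how the value enters the test.

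**The model is one choice among several.** True: the defect is the missing rule. A rank-based analysis could also serve, and the common-SD model has residual bias when spreads differ.

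**Conclusion.** The gap is real and should be closed. The documents set no handling for a post-treatment DLMO outside the sampling window, and the end of that window moves with treatment. If the t-test uses only calculable changes, the loss depends on the primary outcome. The cost ranges from negligible (small shifts, or shifts that track response) to a third of the effect at k = 3 with means of 1 vs 2 h: (60 − 39)/60 = 35%. Confidence is medium, because the shift, the mean advances, the interval spread and the SD of 61 min are all assumed or back-solved.

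Three stronger readings are not supported:
- That the plan excludes these participants. It does not say so; exclusion is one open reading.
- That half the E-DLMO arm will be lost. That follows only in the least favourable case tabulated.
- That the result is biased toward one particular arm under the null. Exclusion is unbiased when both the spread of DLMO change and the distribution of bedtime shifts match across arms. Where they differ, the direction depends on which arm has the larger spread or shift, and the documents do not say.

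**What to change.** Add to section 9.2.1, settled before unblinding:

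1. A post-treatment DLMO not reached by the last valid sample is right-censored at that sample's clock time. One already above threshold at the first valid sample is left-censored at that time. One lost to invalid samples is missing.
2. Change in DLMO is analysed by censored-normal regression, using each participant's own censoring times. Sensitivity analyses: the complete-case t-test, and a version with arm-specific SDs or a rank-based analysis.
3. The numbers censored early and late, and the bedtime shift, are reported by arm. If an arm has fewer than two observed post-treatment values, the model is not interpreted and only the counts are given.

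Cost: analysis wording and slightly more analysis work, with no extra samples or visits. Downsides: a normality assumption; a small upward bias (about 1-3 min in the cases run) if the shift tracks response; and residual bias of the common-SD model when spreads differ. No change to sampling, schedule or dosing is proposed.

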## 7.2 Secondary Assessments

Secondary Assessments: 1. Change from pre- to post-treatment in sleep parameters (total sleep time, initial sleep latency, sleep onset time, sleep offset time) measured using wrist actigraphy and daily sleep diaries; 2. Change in daytime symptoms and functioning (Epworth Sleepiness Scale, Multidimensional Fatigue Inventory-20, Sheehan Disability Scale, Patient Health Questionnaire-9, Generalized Anxiety Disorder-7,) from pre- to post-

treatment, 3. Change in self-report sleep quality and symptoms (as assessed by the Pittsburgh Sleep Quality Index, , Morningness Eveningness Questionnaire, PROMIS-Sleep Disturbance scale, PROMIS-Sleep Related Impairment scale).

**Wrist Actigraphy Assessments:** The Actiwatch Spectrum Plus will be worn by participants daily throughout the protocol for wrist actigraphy monitoring to approximate objective sleep/wake patterns. The Actiwatch Spectrum Plus is a kinesiology ambulatory recorder manufactured by Philips Respironics (Bend, Oregon), and is exempt from FDA premarket submission. Actigraphy data will be scored using Actiware®-Sleep software following standard scoring procedures (Patel et al. 2015).

**Sleep Diary Assessments:** Participants will maintain daily self-report sleep-wake diaries daily throughout the treatment protocol.

**Daytime Symptoms Assessments:** Participants will complete the self-report questionnaires (Epworth Sleepiness Scale, Multidimensional Fatigue Inventory-20, Sheehan Disability Scale, Patient Health Questionnaire-9, Generalized Anxiety Disorder-7,) to assess daytime symptoms.

**Sleep Quality and Symptoms:** Participants will complete the self-report questionnaires (the Pittsburgh Sleep Quality Index, Morningness Eveningness Questionnaire, PROMIS-Sleep Disturbance scale, PROMIS-Sleep Related Impairment scale) to assess sleep quality and symptoms.

**Exploratory Assessment:** Conners Adult ADHD Rating Scale-Short Form (Change from pre- to post-treatment)

## **8 ADVERSE EVENT REPORTING**

### **Adverse Event Definition**

An adverse event (AE) is any untoward medical occurrence in a subject participating in an investigational study or protocol regardless of causality assessment. An adverse event can be an unfavorable and unintended sign (including an abnormal laboratory finding), symptom, syndrome or disease associated with or occurring during the use of an investigational product whether or not considered related to the investigational product.

### **These events may be:**

- a. *Definitely related:* clearly associated with study drug/treatment
- b. *Probably related:* likely associated with study drug/treatment
- c. *Possibly related:* may be associated with study drug or other treatment
- d. *Unlikely to be related,* or
- e. *Definitely not related* to the study drug/treatment

*For reporting purposes, an AE should be regarded as definitely or probably related to the regimen if the investigator believes that at least one of following criteria are met:*

- a. There is a clinically plausible time sequence between onset of the AE and the administration of the study drug or treatment.

- b. There is a biologically plausible mechanism for the study drug or treatment causing or contributing to the AE.
- c. The AE cannot be attributed solely to concurrent/underlying illness, other drugs, or procedures.
- d. A potential alternative cause does not exist.

**Serious Adverse Events (SAE):** An adverse drug experience occurring at any dose that results in any of the following outcomes:

- a. Death
- b. A life-threatening adverse drug experience
- c. Inpatient hospitalization or prolongation of existing hospitalization
- d. A persistent or significant disability &/or incapacity
- e. A congenital anomaly or birth defect

Important medical events that may not result in death, be life-threatening, or require hospitalization may be considered a serious adverse drug experience when, based upon appropriate medical judgment, they may jeopardize the patient or subject and may require medical or surgical intervention to prevent one of the outcomes listed in this definition. A serious adverse experience includes any experience that is fatal or immediately life threatening, results in a persistent or significant disability/incapacity, requires or prolongs in-patient hospitalization, or is a congenital anomaly, cancer, or overdose.

Other important medical events that may not result in death, not be life-threatening, or not require hospitalization may be considered a serious adverse experience when, based upon appropriate medical judgment, the event may jeopardize the subject/patient and may require medical or surgical intervention to prevent one of the outcomes listed previously.

*Expected adverse events are those adverse events that are listed in the protocol and the study informed consent document.*

*Unexpected adverse events are those that are not anticipated in the study informed consent. This includes adverse events for which the specificity or severity is not consistent with the description in the informed consent.*

*Unanticipated problem: Per FDA Procedural Guidance for Clinical Investigators, Sponsors, and IRBs (January 2009), A serious problem that has implications for the conduct of the study (requiring a significant and usually safety-related, change in the protocol such as revising inclusion/exclusion criteria or including a new monitoring requirement, informed consent or investigator's brochure).*

*Unanticipated problem Reporting: Per 21 CFR 312.66, 312.53 (c)(1)(vii), and 56.108(b)(1), should an Unanticipated problem occur during the investigation, the investigator will promptly report all unanticipated problems involving risks to human subjects or others to IRBMED /FDA.*

*The severity or grade of an adverse event may be measured using the following definitions:*

**Mild:** Noticeable to the subject, but does not interfere with subject's expected daily activities, usually does not require additional therapy or intervention, dose reduction, or discontinuation of the study.

**Moderate:** Interferes with the subject's expected daily activities, may require some additional therapy or intervention but does not require discontinuation of the study.

**Severe:** Extremely limits the subject's daily activities and may require discontinuation of study therapy, and/or additional treatment or intervention to resolve.

**Event reporting:** Information regarding potential adverse events (AE) will be collected by participant report at each study assessment/follow-up. [name] will ensure that all protocol deviations, AEs, and SAEs are reported to the IRB and FDA according to the applicable regulatory requirements. AEs will be reported according to the study-specific reporting timeline outlined below. Only related adverse events will be reported.

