**Table 2. Study-Specific AE Reporting Timeline**

Reportable Events	Timing of Report to IRB and FDA
Unanticipated problem involving risks to subjects or others related to this research study	Serious: within 7 days Non-serious: with scheduled continuing review
Any physical, social, or psychological harm attributable to participation in this research study (e.g., an injury occurring during a study visit, infection at the site of a blood draw if antibiotics are required)	Serious: within 7 days Non-serious: with scheduled continuing review
Death while on study regardless of relatedness	Within 7 days
Privacy violation or breach of confidentiality	Within 7 days
Protocol deviations not related to an adverse event	With scheduled continuing review
Unanticipated problem related to the research that is not a serious adverse event	With scheduled continuing review
Expected, minor side effects commonly associated with melatonin use: 

• Dizziness

• Sleepiness

• Headache

• Nausea

• Transient depression

• Insomnia

• Nightmares or vivid dreams

• Diarrhea

• Irritability

	With scheduled continuing review
Other serious events not attributable to the research except death as noted above	With scheduled continuing review

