## **10 MONITORING**

### **10.1 Data and Safety Monitoring Plan**

At each follow-up visit, study staff will query participants about each of the following: review previously reported medications and current use of previously reported medications; any new medications; any side effects from the melatonin; any unexpected medical conditions since their last visit; any new medical diagnoses or changes in medical history since their last visit. Side effects and adverse events will be reviewed with the participant by the study clinician at each follow-up visit. The PI will have oversight of the medical history data, medications, and side effect data for each participant. Only changes to medications/medical history/side effects which occur after the first treatment session/treatment initiation will be recorded. Changes to medications/medical history/side effects deemed by the PI to be possibly, probably, and definitely related to melatonin use will be reported as adverse events.

The PI will be primarily responsible for monitoring data integrity. Monitoring is intended to protect participants' rights and safety, and to ensure the integrity and quality of the data collected. The PI will ensure that all relevant IRBMED and FDA policies, procedures, and stipulations are followed by the study team.

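### The related-only reporting rules in Sections 8 and 10.1 contradict Section 8's own statements and Table 2, which requires reports of unrelated deaths, unrelated serious events and harms from taking part

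*Combined protocol and SAP*

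**What the plan says.** Section 8, under Adverse Event Definition, is broad: "An adverse event (AE) is any untoward medical occurrence in a subject participating in an investigational study or protocol regardless of causality assessment". It repeats that an event counts "whether or not considered related to the investigational product".

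The Event reporting paragraph of Section 8 then gives three instructions in a row. The responsible investigator "will ensure that all protocol deviations, AEs, and SAEs are reported to the IRB and FDA according to the applicable regulatory requirements". AEs follow the timeline in Table 2. Finally, "Only related adverse events will be reported".

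Table 2 has eight rows of reportable events. One is a death during the study whatever its cause, due within 7 days. Another is "Other serious events not attributable to the research except death as noted above", due at continuing review. A third is any harm attributable to taking part in the research, due within 7 days if serious.

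Section 10.1 says that changes in medications, medical history or side effects are recorded only if they occur after treatment begins. Of these, the ones "deemed by the PI to be possibly, probably, and definitely related to melatonin use will be reported as adverse events". Section 10.2 has staff tell the PI at once of potentially related unexpected events, and has the PI informed at once of related SAEs.

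**The concern.** Staff cannot follow all of these instructions together. If they follow the narrow ones, reports that Table 2 demands will not be made, and the reported AE record will hold only events attributed to melatonin.

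Relatedness to melatonin is also an awkward filter for this trial. Section 3 says that the intervention under test is the method of timing the dose, and both arms take the same melatonin. The only risk that Section 8 rates as serious is choking on the saliva swab. That is a procedure harm and has nothing to do with melatonin use.

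**Working it through.** No arithmetic applies beyond counting rows, and the plan states no figure to reproduce. The check sets the rules side by side for five kinds of event.

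| Event | Last sentence of Event reporting, Section 8 | Section 10.1 | Table 2 |
|---|---|---|---|
| Death judged unrelated | Not reported | Not reported as an AE | Within 7 days |
| Other serious event judged unrelated | Not reported | Not reported as an AE | Continuing review |
| Choking on the saliva swab | Unclear: Section 8 grades relation to study drug or treatment | Not reported as an AE, since not related to melatonin use | Within 7 days if serious, otherwise continuing review |
| Non-serious event judged unrelated | Not reported | Not reported as an AE | No row |
| Sleepiness after a dose | Reported | Reported | Continuing review |

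1. **Conflict with Table 2.** The first two lines of the table contradict it directly: 2 of its 8 rows ask for events that the related-only sentence leaves out. The third line conflicts with Section 10.1, because harm from participation is a wider class than harm from melatonin. In all, 3 of 8 rows are affected.

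2. **Conflict within Section 8.** The fourth line does not conflict with Table 2, which has no such row. The conflict there is with the definition and with the sentence that sends all AEs and SAEs to the IRB and FDA. Section 8 also has a five-level relatedness scale that ends in unlikely and definitely not related. Under Section 10.1 no reported AE could carry either of those 2 levels.

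3. **Escalation.** Section 10.2 routes to the PI only unexpected events that may be related and SAEs that are related. A death that staff think unrelated has no stated immediate route to the PI, yet Table 2 allows 7 days for the report.

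4. **Recording window.** Section 10.1 starts recording at the first treatment session, and Table 1 starts AE assessment at Follow-up 1. Baseline home saliva collection comes before both (Section 6.1 and Table 1), so a swab harm at baseline falls outside the recording rule. The post-treatment collection is timed from the bedtime assigned at the final session (Section 7.1). It can therefore fall after the last scheduled AE query.

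**The case against.** The strongest reply is that the plan separates recording from reporting. Section 10.1 puts no relatedness condition on recording changes after treatment start. Staff ask about side effects and new medical conditions at every follow-up, and the study clinician reviews them. The related-only sentence sits in a paragraph about reports to the IRB and FDA, where limiting reports by relatedness can be a deliberate choice. Section 8 also sets a low bar: an event is definitely or probably related if "at least one of following criteria are met", and a plausible time sequence is one of the four criteria.

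Most of this stands. It confines the defect to the reported AE record and shows that many events would pass the filter. It does not remove the clash with Table 2, whose death row applies whatever the cause and whose last row is for serious events not due to the research.

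A reader might infer more, but the documents do not support these four readings:

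- **A biased safety comparison between arms.** Section 9 plans no AE analysis by arm, so none is distorted. Only a summary built later from reported AEs would lack unrelated events.
- **A weakened stopping rule.** Section 12.4.1 is triggered by SAEs possibly related to the intervention. Unrelated events lie outside it by design.
- **Loss of evening sleepiness after early dosing.** Sleepiness has its own entry in Table 2, drowsiness is a listed melatonin effect, and the Section 8 criteria would class it as related.
- **Two rival tests of relatedness.** Section 8 gives criteria for the top two levels of a scale, and Section 10.1 sets a cut-off that starts at possibly. These are different things and can coexist.

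**Conclusion.** The contradiction is real and rests on the text alone. Followed literally, the related-only sentence and Section 10.1 leave unrelated deaths, unrelated serious events and procedure harms such as swab choking unreported as AEs, although Table 2 requires reports of all three. Section 10.2 adds a gap in escalation for serious events thought unrelated.

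The size is 2 of 8 Table 2 rows contradicted outright and a third narrowed by Section 10.1. The number of events affected cannot be estimated, because the documents give no expected event rates.

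Two limits apply. For non-serious unrelated events the inconsistency is internal to Section 8 and does not involve Table 2. Information on changes after treatment start should exist in the study records, so it would be wrong to say that it is lost. The exception is harm during baseline saliva collection, which precedes the recording window. The primary endpoint and its analysis are unaffected.

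The conclusion assumes that staff would apply the narrow sentences as written. Staff who treated Table 2 as overriding would make the required reports, but nothing in the plan says that it does.

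**What to change.** - **Section 8, Event reporting:** delete the related-only sentence, or limit it to non-serious events that Table 2 does not list. Bring the preceding all-AEs sentence into line with whichever is chosen.
- **Section 10.1 and Table 1:** record every AE from the first study procedure, including baseline home saliva collection, through the post-treatment collection. Record relatedness to melatonin and relatedness to study procedures as two attributes, both on the existing five-level scale.
- **Section 10.2:** have staff notify the PI of all deaths and serious events, whatever the presumed cause.
- **Consistency:** reconcile the AE definition, Event reporting, Table 2, Section 10.1 and Section 10.2 in one amendment.
- **Section 9:** add a descriptive listing by arm of all AEs and of related AEs. The plan has none at present.

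The cost is wording and a few extra REDCap rows. Staff already ask these questions at every follow-up. The one added task is to ask about harms from the two home saliva collections.
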